**Table 9: Event and Censoring Rules for Supplementary Analyses of Alternative PFS Estimands**

| Estimand   | Alternative 1                    |  | Alternative 2                                   |  | Alternative 2                                   |  |
|--|----------------------------------|--|---|--|---|--|
| Analysis type  | Supplementary                    |  | Supplementary                                   |  | Supplementary                                   |  |
| Analysis purpose   | Alternate progression definition |  | Alternate progression definition                |  | Evaluate potentially informative censoring      |  |
| Analysis ID  | PFS-EA1-1                        |  | PFS-EA2-1                                       |  | PFS-EA2-2                                       |  |
| Analysis name  | Investigator claims              |  | rPFS or sNPACT                                  |  | rPFS or sNPACT despite missing ATA              |  |
| Estimand endpoint  | Radiographic or clinical PD      |  | Radiographic PD or initiation of systemic NPACT |  | Radiographic PD or initiation of systemic NPACT |  |
| Population   | ITT                              |  | ITT   |  | ITT   |  |
| Situation  | Outcome                          | Date of Outcome                                      | Outcome   | Date of Outcome                                      | Outcome   | Date of Outcome                                      |
| Radiographic PD per RECIST 1.1 per BIRC  | NA                               | NA   | event   | date of recorded PD                                  | event   | date of recorded PD                                  |
| Radiographic PD per RECIST 1.1 per Investigator  | event                            | date of recorded PD                                  | NA  | NA   | NA  | NA   |
| Death  | event                            | date of death  | event   | date of death  | event   | date of death  |
| Intercurrent events (excluding those with Treatment Policy strategy for all estimands) |                                  |  |   |  |   |  |
| Clinical deterioration   | event                            | date of determination of clinical deterioration      | NA  | NA   | NA  | NA   |
| Systemic NPACT (medications)   | event                            | date of first initiation of therapy                  | event   | date of first initiation of therapy                  | event   | date of first initiation of therapy                  |
| Local NPACT for disease under study (medications)                                      | event                            | date of first initiation of therapy                  | censored  | date of last ATA* before first initiation of therapy | censored  | date of last ATA* before first initiation of therapy |
| Surgical resection of target tumor lesion(s)   | event                            | date of last ATA* before target lesion resection     | censored  | date of last ATA* before target lesion resection     | censored  | date of last ATA* before target lesion resection     |
| Local radiation: to soft tissue for disease under study                                | event                            | date of last ATA* before non-target lesion resection | censored  | date of last ATA* before non-target lesion resection | censored  | date of last ATA* before non-target lesion resection |
| Missing data   |                                  |  |   |  |   |  |
| No baseline ATA  | censored                         | date of rand.  | censored  | date of rand.  | censored  | date of rand.  |
| ≥ 2 consecutive missing scheduled ATA immediately prior to analysis event              | censored                         | date of last ATA* before missing visits              | censored  | date of last ATA* before missing visits              | event   | date of last ATA* before missing visits              |
| Observation ongoing  |                                  |  |   |  |   |  |
| None of the above  | censored                         | date of last ATA*                                    | censored  | date of last ATA*                                    | censored  | date of last ATA*                                    |

ATA, adequate tumor assessment; BIRC, blinded independent review committee; ITT, intent-to-treat; NA, not applicable; PD, progressive disease; NPACT, non-protocol anti-cancer therapy (medications including radiopharmaceuticals but excluding local radiation)

Date of recorded PD = see SAP text.

\* or date of randomization if no post-randomization ATA

Blue cells indicate changes from primary analysis.

**Table 10: Definitions for Differential Sensitivity Analyses of PFS to Further Evaluate Potentially Informative Censoring (based on PFS-EP-1)**

|  |   |                |                                       |                         |                                       |                                       |                                       |                |
|--|---|----------------|---------------------------------------|-------------------------|---------------------------------------|---------------------------------------|---------------------------------------|----------------|
| Estimand  | Primary   |                |                                       |                         |                                       |                                       |                                       |                |
| Analysis type   | Sensitivity   |                |                                       |                         |                                       |                                       |                                       |                |
| Analysis purpose  | Differential analyses to explore potentially informative censoring  |                |                                       |                         |                                       |                                       |                                       |                |
| Analysis strategy   | Selected censored subjects in primary analysis reclassified as events, differentially by assigned treatment arm, as shown below (green cells) |                |                                       |                         |                                       |                                       |                                       |                |
| Analysis ID   | PFS-EP-11   |                | PFS-EP-12                             |                         | PFS-EP-13                             |                                       | PFS-EP-14                             |                |
| Censoring category for subjects censored in PFS-EP-1 in PITT Population | Experimental   | Control | Experimental                   | Control          | Experimental                   | Control                        | Experimental                   | Control |
| rPD per INV but not BIRC   | At recorded date of first rPD per INV   |                | At recorded date of first rPD per INV |                         | At recorded date of first rPD per INV | At recorded date of first rPD per INV | At recorded date of first rPD per INV |                |
| Discontinued radiographic assessment for reasons other than rPD and no sNPACT  | At date of last ATA   |                | At date of last ATA                   |                         | At date of last ATA                   |                                       | At date of last ATA                   |                |
| sNPACT prior to rPD per INV or BIRC  |   |                | At date of first sNPACT               | At date of first sNPACT |                                       |                                       | At date of first sNPACT               |                |

ATA, adequate tumor assessment; BIRC, blinded independent review committee; rPD, radiographic progressive disease per RECIST 1.1; INV, investigator; sNPACT, systemic non-protocol anti-cancer therapy (medications including radiopharmaceuticals)

\* or date of randomization if no post-randomization ATA

## 8.2 Control of Type I Error

The multiplicity issue resulting from analysis of two primary endpoints (PFS and ORR) will be addressed by applying a modified Bonferroni procedure (dividing the alpha between the two primary endpoints).

ORR will be tested at the 2-sided 1% alpha significance level and PFS will be tested at the 2-sided 4% alpha significance level.

Additionally, the fallback method for alpha allocation (FDA 2017) will be implemented as follows:

- If the null hypothesis is rejected for ORR its alpha allocation of 1% will be passed to PFS which will then be tested at the 5% level.
- If the null hypothesis is not rejected for ORR, then PFS will be tested at its original alpha allocation of 4%.
- An interim analysis (See Section 8.3) is planned for the second primary endpoint of PFS. The interim analysis will be interpreted at an alpha of 5% only if the primary null hypothesis for ORR is rejected.

The primary objectives of the study will be declared as met if at least one hypothesis is rejected at its respective alpha level. All other statistical evaluations of efficacy will be considered exploratory.

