### **9.9 Control of Type I Error**

The multiplicity issue resulting from analysis of two co-primary endpoints (PFS and ORR) will be addressed by applying a modified Bonferroni procedure (dividing the alpha between the co-primary endpoints).

ORR will be tested at the 2-sided 1%  $\alpha$  level and PFS will be tested at the 2-sided 4% ( $\alpha$ ) significance level.

Additionally, the fallback method for alpha allocation (FDA 2017) will be implemented as follows:

- If the null hypothesis is rejected for ORR its alpha allocation of 1% will be passed to PFS which will then be tested at the 5% level.
- If the null hypothesis is not rejected for ORR, then PFS will be tested at its original alpha allocation of 4%.
- As an interim analysis will be performed for the second co-primary endpoint of PFS, the alpha spending function used to determine the critical values for rejection will be based upon a total alpha of either 5% or 4% conditioned upon whether the null is rejected for ORR or not, respectively (see Section 9.8).

The primary objectives of the study will be declared as met if at least one hypothesis is rejected at its respective  $\alpha$  level. All other statistical evaluations of efficacy will be considered exploratory.

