#### **8.1.1.4 Primary Analysis**

The primary analysis of ORR is based on tumor assessments per BIRC and will include all subjects in the OITT population.

Hypothesis testing for ORR will be performed using the Fisher's exact test at the 2-sided  $\alpha=0.01$  level of significance. If a sufficient number of responders are observed, analysis using the Cochran-Mantel-Haenszel (CMH) method to adjust for stratification factors per IRT may also be conducted.

Point estimates of ORR for each treatment arm, the difference in ORR between the two treatment arms, and associated confidence intervals will be provided. The odds ratio and its confidence intervals will also be shown. The 2-sided 95% and 99% CIs for the point estimate will be calculated using exact methods. The 2-sided 95% and 99% CIs for the difference in ORR between the two treatment arms and for the odds ratio will be calculated by asymptotic methods.

If the p-value for the two-sided Fisher's exact test is less than 0.01 and the point estimate for ORR in the cabozantinib arm is higher than that in the placebo arm, the null hypothesis of no difference in ORR will be rejected and it will be inferred that ORR is superior in the cabozantinib arm compared with the placebo arm.

The study will proceed to full enrollment of 300 subjects irrespective of the results of the ORR analysis in the OITT population.

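### Alpha is recycled only from ORR to PFS; also returning PFS's 4% to ORR would be a free improvement, worth about 2 points of ORR power at the design assumption and more if the true ORR is lower

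*Combined protocol and SAP*

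**What the plan says.** SAP 8.2 sets the two levels: "ORR will be tested at the 2-sided 1% alpha significance level" and "PFS will be tested at the 2-sided 4% alpha significance level". It then gives the recycling rule: "If the null hypothesis is rejected for ORR its alpha allocation of 1% will be passed to PFS", after which PFS is tested at 5%. The other branch, in protocol 9.9, reads "If the null hypothesis is not rejected for ORR, then PFS will be tested at its original alpha allocation of 4" percent. The synopsis carries the same rule. None of the three places says what happens to the 4% once PFS has been rejected.

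The ORR decision is fixed separately. SAP 8.1.1.4 opens its rejection rule with "If the p-value for the two-sided Fisher's exact test is less than 0.01", and protocol 9.2.2.1 uses the same threshold. No other level for ORR appears anywhere.

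On status, SAP 8.2 says "The primary objectives of the study will be declared as met if at least one hypothesis is rejected at its respective alpha level", and protocol 9.9 adds "All other statistical evaluations of efficacy will be considered exploratory". The primary ORR analysis uses the first 100 randomized subjects (OITT). ORR in the full ITT population at the final PFS analysis is descriptive only (SAP 8.1.1.5).

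**The concern.** ORR and PFS are both primary endpoints, yet alpha moves only one way. Suppose PFS is rejected and ORR gives p = 0.02. PFS has then used its 4% successfully and no longer needs it to protect a further PFS test, but ORR is still held to 0.01 and its result is exploratory. A formal claim on one of two primary endpoints is given up without any error-rate reason. It matters most if the true response rate is below the planned 35%, because results between 0.01 and 0.05 are then common.

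**Working it through.** **Inputs.** ORR level 0.01 and PFS level 0.04, two-sided (SAP 8.2). ORR 35% versus 2%, 2:1 allocation, 100 subjects, power above 90% (SAP 2.4). PFS: 193 events, HR 0.61, interim at 43% information (SAP 2.4) with Lan-DeMets O'Brien-Fleming spending (SAP 8.3). Assumption: the 100 OITT subjects split 67:33. The documents fix only the 2:1 ratio and stratified permuted blocks.

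**1. Reproducing the plan's figures.**
- Alpha: 0.01 + 0.04 = 0.05.
- ORR power, pooled normal approximation. Pooled rate = (67 × 0.35 + 33 × 0.02)/100 = 0.2411. Null SE = √[0.2411 × 0.7589 × (1/67 + 1/33)] = 0.0910. Alternative SE = √[0.35 × 0.65/67 + 0.02 × 0.98/33] = 0.0632. Power = Φ[(0.33 − 2.576 × 0.0910)/0.0632] = 93.5%. Exact Fisher enumeration gives 97.0%. Both agree with the stated figure.
- PFS boundaries at 43% information: p = 0.0013 and 0.0496 at total alpha 5%, and 0.0008 and 0.0397 at 4%, as in the tables of SAP 2.4. At each look the 4% boundary is stricter than the 5% boundary.

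**2. Error rate of a two-way rule, by closed testing.**
- Both nulls true: reject the intersection if ORR p < 0.01 or PFS crosses its 4% boundary. The error is at most 0.01 + 0.04 = 0.05, exactly as now.
- ORR null alone: p < 0.05.
- PFS null alone: PFS crosses its 5% boundary.

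A hypothesis is rejected only if its own test and the intersection test both reject. This gives:
- **PFS:** rejected if it crosses the 4% boundary, or if ORR p < 0.01 and it crosses the 5% boundary. This is the present rule, unchanged.
- **ORR:** rejected if p < 0.01, or if p < 0.05 and PFS crosses its 4% boundary. This is the present rule plus the return path.

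Simulation (2,000,000 trials per scenario, group-sequential PFS boundaries, assumed ORR–PFS correlation of 0, 0.4 or 0.7 at the interim) agrees. With both nulls true, the chance of any false rejection is the same under both rules: 0.0494, 0.0489 and 0.0477. With only the ORR null true and PFS certain to reject, the false ORR claim rate goes from 0.010 to 0.050, still within 5%. The simulation uses a normal ORR statistic. The maximum actual size of the Fisher rule in the favourable direction at 67:33 is 0.0043 at nominal 0.01 and 0.022 at nominal 0.05.

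**3. Gain.** Power = Σ over (a, b) of Bin(a; 67, p_cabozantinib) × Bin(b; 33, 0.02), counting tables with two-sided Fisher p below the level and the higher rate on cabozantinib. The 0.05 column applies when PFS is rejected.

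| True cabozantinib ORR | Level 0.01 | Level 0.05 | Difference (points) |
|---|---|---|---|
| 35% (design) | 97.0% | 99.5% | 2.5 |
| 30% | 89.9% | 97.6% | 7.7 |
| 25% | 73.4% | 90.9% | 17.6 |
| 20% | 46.1% | 74.7% | 28.6 |

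Differences are taken from unrounded values.

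On the return path PFS is tested at 4%. With 193 events, its power is Φ[|ln 0.61| × √(193 × 2/9) − 2.054] = Φ(1.18) = 88.2%. Treating the two results as independent, the realised gain at the design values is 0.882 × 2.5 = 2.2 points.

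**4. Sensitivity to the split.** At 67:33 with no placebo responders, 8 to 11 cabozantinib responders give p = 0.0498 to 0.0144, all in the gap. At 68:32, 8 versus 0 and 9 versus 0 give 0.052 and 0.054 and stay outside it. At 65:35, 11 versus 0 gives 0.0074 and already passes. The same enumeration at 35% versus 2% gives 95.4% to 99.5% at 68:32 and 97.4% to 99.7% at 65:35, so the design-value gain given PFS rejection is roughly 2 to 4 points across these splits.

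**The case against.** The plan names the fallback method, applies it as named, keeps familywise error at 5%, and states it consistently in the synopsis, protocol and SAP. Choosing it over a two-way procedure can be called a design preference. That stands to this extent: nothing here is an error or a contradiction. It is not a trade-off either, because the two-way rule loses nothing for PFS and has the same familywise bound.

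The gain is small where the plan expects to be. At the 40% ORR seen in the Phase 2 study of previously treated subjects (protocol 1.4.1.2.1), power goes only from 99.3% to 99.9%. This stands: the larger gains need a true ORR the plan does not assume. Rates below 35% are not remote on the protocol's own evidence, however. That Phase 2 result rests on 10 of 25 subjects, with 0 of 4 responding after two prior VEGFR-targeted therapies, and such subjects are eligible here. The randomized medullary thyroid cancer study gave 28% (protocol 1.4.1.3).

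The estimate is reported in any case: SAP 8.1.1.4 already plans 95% and 99% intervals. That stands too; only the formal status of the claim changes.

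Timing is the firmest objection. The SAP is dated September 2020 against an April 2018 protocol, and the documents do not show that the ORR analysis was still unopened. Relaxing the ORR threshold after unblinded efficacy results are known would not be free.

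**Conclusion.** The point holds as a free improvement. One-way recycling bars any ORR result between 0.01 and 0.05 from a formal claim, and a two-way rule removes that bar within the same 5% bound and with PFS testing untouched. The benefit is about 2 points of ORR power at 35% versus 2%, and 8 to 29 points given PFS rejection at true rates of 30% down to 20%. These sizes assume a split near 67:33, 2% placebo ORR, and a PFS effect near HR 0.61 for the weighting.

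Three stronger readings are tempting, and the documents do not support them:
- **That type I error is uncontrolled.** It is controlled, by the split and the fallback.
- **That a trial with PFS rejected and ORR p = 0.02 fails.** SAP 2.3 and 8.2 require only one rejection, so it has already succeeded. An ORR miss need not block the Maintenance Phase either: SAP 2.1 speaks of both endpoints being successful, but protocol 3.3 asks only that they have been analysed.
- **That ORR could be re-tested at 5% on later or ITT data.** That would be a second look. The argument covers only the single p-value from the planned OITT analysis.

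**What to change.** Before any unblinded efficacy analysis, add to SAP 8.2, protocol 9.9 and the synopsis a rule such as: *If the ORR null is not rejected at 0.01 and the PFS null is later rejected at its 4% boundary (interim or final), the 4% is passed to ORR and the single Fisher p-value from the primary OITT analysis is compared with 0.05; ORR is not re-tested on later or ITT data.*

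Conform the rejection wording in protocol 9.2.2.1 and SAP 8.1.1.4, which otherwise would still hold ORR to 0.01. Align the interval wording in protocol 9.2.2.1, which gives only 99% limits; the SAP already has both levels. Leave every PFS boundary as it is.

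The cost is a short text change in five places. SAP 4.9 already provides for a revised plan before unblinded analyses. There are no extra subjects, no extra look and no loss for PFS. If ORR has already been unblinded, the change should not be made.

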### **8.3 Interim Analyses**

A single interim analysis of PFS is planned at the time of the primary ORR analysis. Approximately 43% of the planned total PFS events are expected to have been observed at that time. Rejection of the null hypothesis for PFS at the interim analysis is not expected; it is intended to allow evaluation of PFS at the time of the primary analysis of ORR. Inflation of Type 1 error arising from repeated analyses of PFS will be controlled by a Lan-DeMets O'Brien Fleming alpha spending function, using the actual information fraction at the interim analysis.

### **8.4 Additional Endpoints**

#### **8.4.1 Overall Survival**

##### **8.4.1.1 Definition**

Duration of OS is defined as the time from randomization to death due to any cause. For subjects who are alive at the time of data cutoff but are permanently lost to follow-up, duration of OS will be right censored at the date the subject was last known to be alive. Those who withdraw consent from survival follow-up and are alive will be right censored at the date the subject withdrew consent from survival follow-up, unless date of death can be obtained from public records. Subjects alive on or after the data cutoff or those who died after the data cutoff will be right censored at the date of data cutoff.

OS (months) = (earliest date of death or censoring – date of randomization + 1)/30.4375

##### **8.4.1.2 Analysis**

The analysis of OS will include all subjects in the OITT and ITT populations.

The summaries (median and 95% CI for median, stratified and unstratified HRs and their 95% CI) and graphs described in Section 8.1.2.6 will be generated for OS. Log-rank p-values will be calculated and will be presented for descriptive purposes; formal inferences will not be drawn.

At the time of the analysis of ORR, if the null hypothesis for ORR is rejected an administrative interim analysis of OS will be performed with the primary purpose of evaluating the potential for detriment to survival with cabozantinib treatment.

A sensitivity analysis for OS will be conducted censoring for receipt of any subsequent anti-cancer therapy in the ITT population.

In addition, exploratory OS analysis will be conducted adjusting for crossover of placebo subjects to cabozantinib as a time-dependent covariate for the ITT population. Additional exploratory OS analysis may also be conducted to adjust for the crossover to cabozantinib utilizing the inverse probability of censoring weights (IPCW) or rank preserving structural failure time model (RPSFTM), if feasible.

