### **1.5.4 Rationale for Placebo**

Randomized, double-blind studies with a placebo control have been used in prior DTC studies using VEGFR TKIs as the experimental arm (Schlumberger et al 2015; Brose et al 2014). This design allows for evaluation of the natural history of advanced DTC in placebo-treated subjects of the comparator arm as well as the true effects of the tested agent in the experimental arm. In this study, the lack of available treatment options in patients with DTC who had received prior VEGFR-TKI therapy supports the use of a randomized, double-blind study design with a placebo arm. A 2:1 randomization schedule will be employed to minimize the number of subjects randomized to placebo. All subjects will receive BSC in addition to the randomized study treatment. For subjects randomized to the placebo arm, crossover to receive cabozantinib will be allowed after radiographic progression has been confirmed by the BIRC.

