#### **Inclusion Criteria**

1. Not applicable
2. Not applicable
3. Not applicable
4. Not applicable
5. Not applicable
6. Recovery to baseline or  $\leq$  Grade 1 (CTCAE v5) from toxicities related to any prior treatments, unless AE(s) are clinically nonsignificant and/or stable on supportive therapy
7. Not applicable
8. Eastern Cooperative Oncology Group performance status (ECOG PS) of 0 or 1

9. Adequate organ and marrow function based upon meeting all of the following laboratory criteria within 7 days before crossover:
  - a. Absolute neutrophil count  $\geq 1500/\text{mm}^3$  ( $\geq 1.5 \text{ GI/L}$ ) without receipt of granulocyte colony-stimulating factor support within 2 weeks before screening laboratory sample collection
  - b. Platelets  $\geq 100,000/\text{mm}^3$  ( $\geq 100 \text{ GI/L}$ ) without receipt of transfusion within 2 weeks before screening laboratory sample collection
  - c. Hemoglobin  $\geq 9 \text{ g/dL}$  ( $\geq 90 \text{ g/L}$ ) without receipt of transfusion within 2 weeks before screening laboratory sample collection
  - d. Alanine aminotransferase (ALT), AST, and alkaline phosphatase (ALP)  $\leq 3 \times \text{ULN}$ . ALP  $\leq 5 \times \text{ULN}$  if the subject has documented bone metastases
  - e. Bilirubin  $\leq 1.5 \times \text{the ULN}$ . For subjects with known Gilbert's disease  $\leq 3 \times \text{ULN}$
  - f. Serum creatinine  $\leq 2.0 \times \text{ULN}$  or calculated creatinine clearance  $\geq 30 \text{ mL/min}$  ( $\geq 0.5 \text{ mL/sec}$ ) using the Cockcroft-Gault (see Table 5-2 for Cockcroft-Gault formula)
  - g. Urine protein/creatinine ratio (UPCR)  $\leq 1 \text{ mg/mg}$  ( $\leq 113.2 \text{ mg/mmol}$ )
10. Must be receiving thyroxine suppression therapy, and TSH must be below the lower cutoff of the reference range or less than 0.50 mIU/L ( $< 0.50 \mu\text{IU/mL}$ ), whichever is lower, within 28 days before crossover.  
(*Note: If hormone replacement therapy is tolerated a TSH level of  $\leq 0.1 \text{ mIU/L}$  should be targeted.*)
11. Not applicable
12. Not applicable
13. Not applicable

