## 2 STUDY DESCRIPTION

### 2.1 Study Design

This is a Phase 3 multicenter, randomized, double-blinded, placebo-controlled trial of cabozantinib in subjects with radioiodine (RAI) refractory differentiated thyroid cancer (DTC). Best supportive care (BSC) will be provided for subjects on both treatment arms. The multiple primary efficacy endpoints for the study are progression-free survival (PFS) and objective response rate (ORR) assessed per blinded independent radiology committee (BIRC). Approximately 300 subjects will be randomized in a 2:1 ratio to receive either cabozantinib or placebo.

Each subject's course of treatment will consist of the following periods:

**Pre-treatment Period:** Potential subjects will be screened to determine if they meet the required eligibility criteria. Qualifying screening assessments must be performed within 28 days before randomization unless otherwise specified.

**Treatment Period:** Subjects who meet all study eligibility criteria will be randomly assigned in a 2:1 ratio to receive blinded study treatment cabozantinib or placebo. Subjects on both treatment arms will be treated with BSC. This excludes non-protocol anticancer therapy (NPACT).

**Crossover Phase:** As subjects in the study population have limited treatment options, and to minimize the potential for differential dropout among subjects randomized to placebo with respect to the PFS endpoint as assessed by BIRC, the study will allow eligible subjects randomized to placebo to crossover to receive cabozantinib upon experiencing radiographic disease progression (PD) per RECIST 1.1 that is confirmed by the BIRC. To facilitate this:

- A real-time dual-reader adjudicated BIRC review of radiographic images per RECIST 1.1 will be employed to document objective radiographic progression contemporaneously with subject study participation.
- At the time of investigator-determined radiographic progression per RECIST 1.1, investigators may request from the Sponsor's medical monitor (or designee) confirmation of BIRC-determined radiographic PD.
- For subjects with BIRC-confirmed radiographic progression:
  - Upon authorization from Sponsor's medical monitor (or designee), investigators may unblind individual subjects via the Interactive Response Technology (IRT) system.
  - Unblinded subjects randomized to placebo have the following options:

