#### 8.4.4 Time to Second Disease Progression or Death (PFS2)

The time to second disease progression or death (PFS2) is defined as the time from randomization to the date of the earliest of the following events: start of second subsequent non-radiation anti-cancer therapy, second objective disease progression, or death. For placebo subjects who have crossed over to receive cabozantinib, cabozantinib will be considered as the first subsequent therapy. For subjects randomized to cabozantinib who continue on study treatment after their first disease progression, the start date of their first subsequent therapy will be considered to be a potential event date. Subjects alive and for whom a PFS2 event has not been observed will be censored at the last time known to be alive. The definition of event dates for PFS2 is provided in the table below.

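### The committed crossover-adjusted OS analysis models crossover as a time-dependent covariate with no progression term, so it is confounded by progression and fitness and can show a survival harm that does not exist

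*Combined protocol and SAP*

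**What the plan says.** SAP 8.4.1.2 plans the following for OS beyond the stratified ITT summaries:

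- A committed crossover adjustment: "exploratory OS analysis will be conducted adjusting for crossover of placebo subjects to cabozantinib as a time-dependent covariate for the ITT population". No progression term is named. The form of the model is not given either: it could hold an arm term plus a crossover term, or a single current-treatment indicator.
- Optional alternatives: "Additional exploratory OS analysis may also be conducted to adjust for the crossover to cabozantinib". The methods named are IPCW and RPSFTM, subject to a feasibility condition that is not defined.
- A second committed analysis: "A sensitivity analysis for OS will be conducted censoring for receipt of any subsequent anti-cancer therapy in the ITT population". It does not say whether crossover cabozantinib counts. For PFS2 (SAP 8.4.4) it does: "cabozantinib will be considered as the first subsequent therapy".

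Access to crossover is tied to progression. Protocol 1.5.4 says that "crossover to receive cabozantinib will be allowed after radiographic progression has been confirmed by the BIRC", and SAP 2.1 restricts it to "eligible subjects randomized to placebo to crossover to receive cabozantinib upon experiencing radiographic disease progression (PD) per RECIST 1.1" with BIRC confirmation. Protocol Appendix B adds fitness criteria, among them "Eastern Cooperative Oncology Group performance status (ECOG PS) of 0 or 1", organ function limits and a list of exclusions. Crossover without progression becomes possible only when the whole study is unblinded (protocol 3.3, Maintenance Phase; SAP 2.1).

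The final OS analysis is done at the primary PFS analysis (protocol 9.3). Its p-values are descriptive.

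**The concern.** A time-dependent covariate adjusts validly for crossover only if, at each time, subjects who cross over have the same death risk as those who do not. Here the switch follows a strong prognostic event. Once a placebo subject progresses and crosses over, the later person-time leaves the placebo reference. Progressed subjects in the cabozantinib arm stay in that arm's risk set. The arm coefficient then compares cabozantinib before and after progression with a placebo reference depleted of post-progression time. If death is more likely after progression, the HR moves up even when the drug does nothing to survival.

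Fitness selection acts on the same comparison from the other side, because progressors who are too unfit to cross over remain in the reference.

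What is at stake is a misleading supportive result. The protocol suggests that crossover may explain why two earlier placebo-controlled DTC trials showed no OS benefit (synopsis rationale and section 1.3), so readers will look for a crossover-adjusted estimate. The one the SAP guarantees is open to this confounding.

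**Working it through.** **Inputs from the documents.** 300 subjects, 2:1, 20 per month over 15 months; median PFS 5.5 months (placebo) and 9.0 months (cabozantinib); 193 PFS events at about month 20 (SAP 2.4). Median OS of 34.7 months from the single-arm phase 2 study (protocol 1.4.1.2.1) sets the death rate.

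**Assumptions.** The documents give no crossover rate and no death hazard before or after progression. I take a death hazard multiplied by k after progression (k = 1, 2, 3, 5), crossover in 80% of progressed placebo subjects, and a 1-month lag from progression to crossover.

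**Step 1: reproduce the plan's timing.** With exponential PFS at rate λ = ln 2 / median, expected events at month 20 are N × [1 − (e^(−5λ) − e^(−20λ)) / (15λ)].

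- Cabozantinib, λ = 0.0770: 200 × 0.5965 = 119.3
- Placebo, λ = 0.1260: 100 × 0.7608 = 76.1

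The total is 195, against the stated 193.

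**Step 2: the mechanism by hand.** Take the null with median PFS of 5.5 months in both arms, k = 3 and follow-up month 8, ignoring deaths. The progression-free share is e^(−0.126×8) = 0.365. The share that progressed within the last month is 0.049, and the share that progressed earlier is 0.586. With pre-progression hazard h:

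- Cabozantinib arm: h × (0.365 + 3 × 0.635) = 2.27h.
- Placebo not crossed over: 0.365 progression-free, plus 0.049 + 0.2 × 0.586 = 0.166 progressed. The mean hazard is h × (0.365 + 3 × 0.166) / 0.531 = 1.63h.

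The ratio is 2.27 / 1.63 = 1.4, with no drug effect. The same sum gives 1.13 at month 2 and 1.29 at month 4.

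**Step 3: simulation under the null.** Illness-death model, equal progression in both arms, no drug effect on death, month-20 cutoff, about 50 to 57 deaths per 300 subjects. HRs come from 240,000 subjects. False-harm rates (z > 1.96) come from 1,500 trials of 300. ITT gave 0.99 to 1.00.

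| k | Arm HR, arm + crossover(t) | HR, current-treatment coding | HR, censored at crossover | False harm, arm + crossover(t) | False harm, ITT |
|---|---|---|---|---|---|
| 2 | 1.15 | 1.19 | 1.15 | 4.0% | 1.7% |
| 3 | 1.26 | 1.32 | 1.25 | 6.7% | 1.2% |
| 5 | 1.38 | 1.46 | 1.37 | 9.1% | 2.1% |

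With k = 1 the arm HR is 1.00, so progression is the source. At k = 3, 50% crossover gives 1.13 and 100% gives 1.49.

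**Step 4: a real benefit through delayed progression** (medians 9.0 and 5.5 months, k = 3). ITT gives 0.86 and the arm + crossover model gives 1.10, so the direction reverses.

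**Step 5: fitness selection.** If 20% to 40% of progressed subjects are unfit, with doubled hazard, and barred from crossover, the arm HR at k = 3 runs from 1.11 down to 1.00 at month 20, and from 1.00 down to 0.92 at a month-40 cutoff. Variant runs of the same idea gave 1.03 to 1.14.

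**Step 6: the alternatives on null data** (k = 3, 80% crossover).

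| Method | Month 20 | Month 40 |
|---|---|---|
| Arm + crossover(t), arm HR | 1.27 | 1.25 |
| IPCW on progression, HR | 1.00 | 1.00 |
| Arm + crossover(t) + progression(t), arm HR | 0.99 | 1.00 |
| RPSFTM time ratio | 1.01 | 1.00 |

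These hold when progression is the only confounder and, for IPCW, is measured.

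**The case against.** **The analysis is exploratory.** No alpha is attached, no decision rule uses it, and the main OS result compares the randomized arms. This stands, and it limits the consequence. A reader might infer that the trial's check for survival detriment is compromised. The documents do not support that: the detriment look is the administrative interim OS analysis at the time of the ORR analysis, and SAP 8.4.1.2 does not attach the crossover-adjusted model to it.

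**The direction is not fixed.** A reader might infer that the model must move toward harm. Step 5 shows otherwise, since the Appendix B criteria can offset or reverse the bias. This stands too. A model whose error depends on two opposing, unquantified selections is still a poor choice for the one guaranteed adjustment.

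**The size can be overstated.** An arm HR near 1.7 can be produced with a 5-fold hazard jump (0.008 to 0.04 per month) and 80% crossover, but only if crossover is immediate at progression (1.68). With a 1-month lag it is 1.41. BIRC confirmation, authorization, unblinding, separate consent and screening make some lag unavoidable.

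**The better methods are already named and have limits.** This is true. RPSFTM assumes the same effect for drug started after progression as at randomization, and IPCW assumes no unmeasured confounding. One run with k = 3 gave roughly 24 placebo deaths at month 20, so intervals will be wide. This argues for stating the limits. It does not argue for guaranteeing the confounded method.

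**A progression term may be intended.** The SAP is silent. Adding one removes the bias in the simple null case, but the text as written does not call for it.

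**Conclusion.** The point holds as a correction to an exploratory analysis. Under no drug effect on death, with assumed k of 2 to 5, 80% crossover and a 1-month lag, the committed model gives an arm HR of about 1.15 to 1.5 depending on its coding, against an ITT HR near 1.0. Falsely significant harm appears in 4.0% to 9.1% of trials at month 20 under the arm + crossover form. A benefit through delayed progression can be hidden or reversed. The hazards and crossover rates are assumptions; the accrual, allocation and PFS medians are the plan's own.

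Two further inferences go too far. Crossover is not confined to progressed subjects throughout, because study-wide unblinding opens it without progression; this would mostly follow the final OS analysis. Nor is it certain that this is the only committed analysis that handles crossover: if crossover cabozantinib counts as subsequent anticancer therapy, the committed censoring analysis is a second one, with nearly the same bias (1.15 to 1.37), so it does not rescue the plan.

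**What to change.** In SAP 8.4.1.2:

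1. Make RPSFTM with re-censoring the committed crossover-adjusted OS analysis.
2. Add IPCW as supportive, with time-varying progression and fitness covariates such as ECOG PS in the weight model.
3. Drop the time-dependent covariate model. If it is kept, give its exact form and label it as confounded by progression and not an estimate of the treatment effect.
4. State whether crossover cabozantinib counts as subsequent anticancer therapy in the OS censoring analysis. If it does, give that analysis the same caution.

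The cost is wording and modest programming. Open-label registration dates in IRT, BIRC progression and scheduled ECOG PS are already collected. The common-effect and no-unmeasured-confounding assumptions should be stated with the results. Intervals will be wide with few placebo deaths, and the analysis stays exploratory.
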